### 3.2.2. **Electrocardiograms (ECG)**

ECG recordings will be obtained after the subject has been supine and at rest for approximately 3 minutes. Additional 12-lead ECGs may be obtained at the investigator's discretion and should always be obtained in the event of an early termination. The ECG will be repeated if any results are considered to be clinically significant. Any clinically significant changes occurring during the trial will be recorded in the AE section of the eCRF.

At Screening, triplicate 12-lead ECGs are required to assess subject eligibility. A triplicate set of ECGs is 3 consecutive ECGs collected 1 to 2 minutes apart over a 5-minute period. The central ECG service will provide the QTcF corrections and average of the 3 ECGs performed to determine eligibility.

At all other specified time points in the Schedule of Assessments ([Section 9.1](#)), where an ECG recording must be performed, only a single ECG is required.

### 3.2.3. **Clinical Safety Laboratory Assessments**

The clinical laboratory tests as listed in the protocol will be performed in accordance with the laboratory manual and the Schedule of Assessments ([Section 9.1](#)). All laboratory tests with values considered clinically significantly abnormal during participation in the trial should be repeated until the values return to normal or baseline or are no longer considered clinically significant by the investigator or medical monitor. If clinically significant values do not return to normal/baseline within a period of time judged reasonable by the investigator, the etiology should be identified, and the medical monitor notified.

### 3.2.4. **Vital Signs**

Vital signs include systolic and diastolic blood pressures, heart rate, respiratory rate, and body temperature. Triplicate blood pressure and heart rate measurements will be obtained after the subject has been supine and at rest for at least 3 minutes. Measurements will be obtained at approximately 1-minute intervals at the time points indicated in the Schedules of Assessments ([Section 9.1](#)). The triplicate values will be individually recorded, and the values will be averaged by the sponsor for all time point assessments following confirmation of eligibility. For determination of eligibility, the average of the last 2 values will be used.

The supine measurements will be followed by a single measurement in the standing position (after standing for approximately 2 minutes) to allow for orthostatic assessments. Orthostatic hypotension is defined as a decrease of  $\geq 20$  mmHg in systolic blood pressure and/or  $\geq 10$  mmHg in diastolic blood pressure upon standing compared with the average of the resting supine blood pressure measurement (as measured above).

### 3.2.5. **Physical and Neurological Examinations**

A full physical examination will include a review of the following body systems: head, ears, eyes, nose, mouth, skin, heart and lungs, lymph nodes, gastrointestinal, and musculoskeletal systems.

A limited physical examination will include evaluation of cardiovascular, pulmonary, and gastrointestinal systems.

A full neurological examination will include an assessment of the subject's mental status (level of consciousness, orientation, speech, memory, etc), cranial nerves, motor (muscle appearance, tone, strength, and reflexes), sensation (including Romberg sign), coordination, and gait.

### **3.2.6. Columbia-Suicide Severity Rating Scale (C-SSRS)**

Suicidality will be monitored during the trial using the C-SSRS.

This trial will use the "Baseline/Screening" and "Since Last Visit" versions of the scale. The "Baseline/Screening" version will be completed for all subjects at Screening to determine eligibility.

The "Since Last Visit" C-SSRS form will be completed after the Screening visit. The investigator will review the results of the "Since Last Visit" C-SSRS during the trial to determine whether it is safe for the subject to continue in the trial. If a subject has any "YES" answers on the C-SSRS for the suicidal ideation or suicidal behavior items, the investigator will evaluate whether a risk assessment by a qualified mental health professional (or the investigator alone if the investigator is a qualified mental health professional) is needed and discuss with the medical monitor whether the subject should continue in or be discontinued from the trial.

Details of C-SSRS categories as well as definition of treatment emerging events are provided in [Section 9.2](#).

### **3.2.7. Prior Medications, Concomitant Medications and Medications Taken Post Last Dose of IMP**

Prior medications are those medications taken prior to and ended prior to the initiation of IMP. Concomitant medications are those medications taken on or after the initiation of IMP. These medications include those medications started before the initiation of IMP and continuing post Day 1. Medications that start after the last dose of IMP will be classified as taken post last dose and will not be considered as concomitant. These medications will be recorded in the CONCOMITANT MEDICATIONS eCRF.

### **3.2.8. Prior Non-Drug Therapy/Procedures, Concomitant Non-Drug Therapy/Procedures, and Non-Drug Therapy/Procedures Taken Post Last Dose of IMP**

Prior non-drug therapy/procedures are those therapies/procedures taken prior to and ended prior to the initiation of IMP. Concomitant non-drug therapy/procedures are those therapy/procedures taken on or after the initiation of IMP. These procedures include those procedures started before the initiation of IMP and continuing post Day 1. Procedures that start after the last dose of IMP will be classified as taken post last dose and will not be considered as concomitant. These procedures will be recorded in the NON-DRUG THERAPY AND PROCEDURES eCRF.

### **3.2.9. Extrapyramidal Symptoms (EPS)**

EPS are serious side-effects of antipsychotic and other drugs. These symptoms can include parkinsonism, akathisia, dyskinesia, and other movement disorders. Rating scales such as the SAS, BARS, and AIMS can be used to assess the severity of the symptoms.

### 3.2.9.1. Simpson-Angus Scale (SAS)

The SAS ([Simpson and Angus, 1970](#)) consists of a list of 10 symptoms of parkinsonism (gait, arm dropping, shoulder shaking, elbow rigidity, wrist rigidity, head rotation, glabella tap, tremor, salivation, and akathisia). Each item is rated on a 5-point scale, with a score of 0 representing absence of symptoms and a score of 4 representing a severe condition. The SAS total score is the sum of the scores for all 10 items.

In case of missing item scores from the SAS, the missing value will be replaced by the sum of the non-missing scores at the same visit from the same subject multiplied by the expected number of item scores (i.e., 10) and divided by the actual number of item scores contributing to the total score. In case all item scores are missing, the total score will be set as missing.

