8.1 Efficacy Assessments

Trained and qualified (details provided in the Operations Manual) clinicians should administer the efficacy assessments and the number of raters should be kept to a minimum. All efforts should be made to ensure the same clinician administers the scales for a given participant throughout the trial.

All efficacy assessments will be completed using an approved electronic data capture system.

Benzodiazepines and non-benzodiazepine sleep aids are not permitted within 12 hours of administration of clinician-administered scales (see [Section 6.7](#)).

The timing and frequency of efficacy assessments are provided in the Schedule of Assessments ([Section 1.3](#)).

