### **3.1.1.4. Handling of Missing Items from PANSS**

If individual items are missing from a given subscale of PANSS for an individual subject at a given time point, the subscale total will be calculated by prorating the total of non-missing items if the number of missing items is no more than one item of the total number of items in the subscale. The PANSS total for an individual subject at a given time point will be similarly calculated by prorating the total of non-missing items if the number of missing items is no more than three items. If the number of missing items exceeds the specifications above, the subscale score or the total score for the individual subject at that time point will be considered missing.

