### 3.2.9.3. Abnormal Involuntary Movement Scale (AIMS)

The AIMS assessment ([Guy, 1976](#)) consists of 10 items describing symptoms of dyskinesia. Facial and oral movements (items 1 through 4), extremity movements (items 5 and 6), and trunk movements (item 7) are observed unobtrusively while the subject is at rest, and the investigator also makes global judgments on the subject's dyskinesias (items 8 through 10). Each item is rated on a 5-point scale, with a score of 0 representing absence of symptoms (for item 10, no awareness), and a score of 4 indicating a severe condition (for item 10, awareness, severe distress). In addition, the AIMS includes 2 yes/no questions that address the subject's dental status.

The AIMS Movement Rating Score is defined as the sum of items 1 through 7.

In case of missing item scores from the AIMS, the missing value will be replaced by the sum of the non-missing scores at the same visit from the same subject multiplied by the expected number of item scores (i.e., 7) and divided by the actual number of item scores contributing to the total score. In case all item scores are missing, the total score will be set as missing.

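### As written, the SAS and AIMS missing-item rule puts a prorated total in the place of one item, and neither scale has a minimum number of answered items

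*SAP*

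**What the plan says.** SAP 3.2.9.1 defines the SAS score: "The SAS total score is the sum of the scores for all 10 items". On the item range it says: "Each item is rated on a 5-point scale, with a score of 0 representing absence of symptoms and a score of 4". For missing item scores, "the missing value will be replaced by the sum of the non-missing scores at the same visit from the same subject". The sentence then scales that sum by 10, the full item count, over the count of items answered. The only condition under which no total is produced is the last one: "In case all item scores are missing, the total score will be set as missing".

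SAP 3.2.9.3 repeats the rule for the AIMS Movement Rating Score (items 1 to 7) with the factor changed: "multiplied by the expected number of item scores (i.e., 7) and divided by the actual number of item scores contributing to the total score". It has the same all-items-missing stop.

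SAP 3.1.1.4 handles PANSS differently. There the score being prorated is named as the subscale total or the overall total. A subscale may lack one item, and the 30-item total is prorated only "if the number of missing items is no more than three items". Beyond those limits the score is missing.

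SAP 5.15.8 summarises the SAS and AIMS totals and compares their change from baseline with placebo in an MMRM. Protocol 8.2.7 describes both scales but gives no missing-item rule.

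**The concern.** There are two faults. First, the sentence opens with missing item scores and then replaces the missing value, so on its plain wording an item is being filled in. The formula, however, returns a whole-scale total. A programmer who follows the text would put that total in the item's place and then add the answered items to it again.

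Second, no minimum number of answered items is set. A single item is enough to generate a 10-item SAS total or a 7-item AIMS total, although the same SAP sets a limit for PANSS.

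Change on SAS and AIMS is among the listed secondary safety endpoints, with only Week 3 and Week 6 or early termination scheduled after Baseline. The risk is that some totals are wrong, or that two programmers derive different totals from the same sentence.

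**Working it through.** The documents state no figure for this point, so there is none to reproduce. The rule itself can be worked through.

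**Inputs.** K = expected items: 10 for SAS (SAP 3.2.9.1), 7 for AIMS (SAP 3.2.9.3). Item range 0 to 4, so scale maxima are 10 × 4 = 40 and 7 × 4 = 28. Let k = items missing, m = K − k items answered, S = sum of the answered items.

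**Formulas.**
- Prorated total: S × K/m.
- Literal rule: each missing item takes S × K/m, so the total is S + k × S × K/m.
- Literal ÷ prorated: (m + kK)/K, which is 1 + 0.9k for SAS and 1 + 6k/7 for AIMS.
- Largest overstatement of the true total by proration alone (all unanswered items truly 0): K/m.

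| Scale | Missing (k) | Answered (m) | Prorated ÷ S | Literal ÷ S | Literal ÷ prorated |
|---|---|---|---|---|---|
| SAS | 1 | 9 | 1.11 | 2.11 | 1.90 |
| SAS | 2 | 8 | 1.25 | 3.50 | 2.80 |
| SAS | 5 | 5 | 2.00 | 11.00 | 5.50 |
| SAS | 9 | 1 | 10.00 | 91.00 | 9.10 |
| AIMS | 1 | 6 | 1.17 | 2.17 | 1.86 |
| AIMS | 2 | 5 | 1.40 | 3.80 | 2.71 |
| AIMS | 4 | 3 | 2.33 | 10.33 | 4.43 |
| AIMS | 6 | 1 | 7.00 | 43.00 | 6.14 |

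**Literal reading, one item missing, all items scored 1.** SAS: S = 9, imputed item 9 × 10/9 = 10, total 9 + 10 = 19; the prorated total is 10. AIMS: S = 6, imputed item 6 × 7/6 = 7, total 6 + 7 = 13; the prorated total is 7.

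**Impossible values, literal reading, one item missing.** The imputed SAS item exceeds 4 when S > 4 × 9/10 = 3.6, and the AIMS item when S > 4 × 6/7 = 3.43. Both happen from S = 4. The total passes its scale maximum from S = 19 (SAS) and S = 13 (AIMS).

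**Prorated-total reading.** One missing item can overstate the true total by at most 10/9 = 1.11 (SAS) or 7/6 = 1.17 (AIMS). With no minimum, the overstatement can reach 2-fold or more once 5 or fewer SAS items (10/5 = 2.0) or 3 or fewer AIMS items (7/3 = 2.33) are answered. One answered SAS item scored 1 becomes 1 × 10/1 = 10. The literal rule would give 1 + 9 × 10 = 91 in that case, above the maximum of 40.

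**Scale of effect on an arm mean.** Assume about 124 participants per arm, the number planned for randomization. One SAS total wrong by 19 − 10 = 9 points moves the raw mean by 9/124 = 0.07. One total with S = 1 and one item missing (2.11 against 1.11) moves it by 1/124 = 0.008.

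**The case against.** The strongest reply is that the formula is the usual one for a prorated total. It divides by the number of items contributing to the total, and the next sentence is about the total. As an item value it makes no sense, because it can exceed the item's maximum. On this view the text has a slip of one word. This largely stands as an account of intent, and on that reading the near-doubling with one missing item disappears. The wording still needs correcting, because the only thing described as missing is an item score, and the section names the total when it means the total.

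SAP 9.4 also requires independent programming and statistician review, which might expose the error. That helps when an item is scored above 4. It helps less for small sums: S = 3 gives an imputed item of 3.33 (SAS) or 3.5 (AIMS), inside the range. Verification does nothing about the lack of a minimum item count, which follows from the rule on any reading.

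The effect is also limited by low scores. Protocol 5.1 requires every SAS item and AIMS items 1 to 7 to be below 2 at consent and Baseline. The error is multiplicative, and answered items summing to 0 give 0 on both readings. A reader might infer that scores near zero make the arm means fragile. The arithmetic points the other way, since the error is small or nil there.

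A reader might also infer that EPS scales are exposed to missing items because the protocol says "All efficacy assessments will be completed using an approved electronic data capture system" and has no such sentence for EPS. That silence does not show paper collection; Protocol 10.1.6 puts participant data on the eCRF or in electronic transfer. Equally, it gives no assurance that every item is answered, and the SAP itself provides for missing items.

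**Conclusion.** The rule is wrong as written, and on the likely intended reading it remains incomplete. Taken literally, one missing item gives 1.90 times (SAS) or 1.86 times (AIMS) the prorated total, and item scores above 4 once the answered items sum to 4 or more. Read as proration of the total, that error goes. What remains is that one answered item can stand for the whole scale, with overstatement of up to 10-fold (SAS) or 7-fold (AIMS) if the unanswered items are truly 0.

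The consequence is minor. Only the SAS and AIMS results in SAP 5.15.8 are touched; the primary and key secondary endpoints are not. No missing-item rate is given, so the effect on arm means cannot be calculated, and it is probably small.

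Two stronger conclusions are not supported. The documents do not show that reported EPS totals will be doubled, because that needs both missing items and literal coding. Nor do they present EPS as the trial's central tolerability claim: it is one of several secondary safety endpoints, and there is no active comparator.

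**What to change.** In SAP 3.2.9.1 and 3.2.9.3, replace the missing-item sentence and the all-items-missing sentence with a rule of this form: if no more than a stated number of items is missing, the total score equals the mean of the non-missing items multiplied by 10 (SAS) or by 7 (AIMS items 1 to 7); otherwise the total is missing.

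One missing item is a reasonable limit by analogy with PANSS. One of 10 for SAS is the same 10% as 3 of 30 for the PANSS total, and one of 7 for AIMS matches the one-item allowance on the 7-item PANSS positive and negative subscales. It would hold the largest overstatement to 1.11 (SAS) and 1.17 (AIMS). The exact limit is the sponsor's choice, but it should be fixed before unblinding.

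The cost is a change of wording in two SAP sections and a few totals that become missing.

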### 3.2.9.2. Barnes Akathisia Rating Scale (BARS)

The BARS ([Barnes, 1989](#)) consists of 4 items related to akathisia: objective observation of akathisia by the investigator, subjective feelings of restlessness by the subject, subjective distress due to akathisia, and global clinical assessment of akathisia. The first 3 items are rated on a 4-point scale, with a score of 0 representing absence of symptoms and a score of 3 representing a severe condition. The global clinical evaluation is made on a 6-point scale, with a score of 0 representing absence of symptom and a score of 5 representing severe akathisia. To complete this scale, subjects are observed while they are seated and then standing for a minimum of 2 minutes in each position. Symptoms observed in other situations (eg, while engaged in neutral conversation or engaged in other activity) may also be rated. Subjective phenomena are to be elicited by direct questioning.

### 3.2.9.3. Abnormal Involuntary Movement Scale (AIMS)

The AIMS assessment ([Guy, 1976](#)) consists of 10 items describing symptoms of dyskinesia. Facial and oral movements (items 1 through 4), extremity movements (items 5 and 6), and trunk movements (item 7) are observed unobtrusively while the subject is at rest, and the investigator also makes global judgments on the subject's dyskinesias (items 8 through 10). Each item is rated on a 5-point scale, with a score of 0 representing absence of symptoms (for item 10, no awareness), and a score of 4 indicating a severe condition (for item 10, awareness, severe distress). In addition, the AIMS includes 2 yes/no questions that address the subject's dental status.

The AIMS Movement Rating Score is defined as the sum of items 1 through 7.

In case of missing item scores from the AIMS, the missing value will be replaced by the sum of the non-missing scores at the same visit from the same subject multiplied by the expected number of item scores (i.e., 7) and divided by the actual number of item scores contributing to the total score. In case all item scores are missing, the total score will be set as missing.

## 3.3. Pharmacokinetics

Venous blood samples will be collected in appropriately labeled tubes, at the times specified in the Schedule of Assessments ([Section 9.1](#)), to evaluate the PK of emraclidine and its metabolite CV-0000364.

All PK samples should be obtained at the exact nominal time relative to dosing. Samples obtained within 20% of the nominal time point (eg, within 12 minutes of a 60-minute sample) will not be considered a protocol deviation, as long as the exact time of sampling is captured in the source documents.

A fully validated bioanalytical method will be used to quantitate the concentrations of emraclidine and CV-0000364 (metabolite) in plasma.

## 4. DATA CONVENTIONS AND VISIT WINDOWS

### 4.1. Data Conventions

#### 4.1.1. Age

Age is the age at the time of informed consent and is as captured on the eCRF.

#### 4.1.2. Day 1 (Baseline)

Day 1 is the day IMP is first initiated.

#### 4.1.3. Study Day of an Event

Study Day of an event is defined relative to Baseline (Day 1) as:

Study Day = event date – date of Day 1 (+ 1, if event date  $\geq$  date of Day 1).

This calculation will result in negative study days for an event occurring prior to the start of IMP and positive study days for an event on or after the start of IMP. There will be no Day 0 value to match the schedule of events.

#### 4.1.4. Days on Study

Days on Study is the number of days from Day 1 to the date of study completion or early termination as recorded on the END OF STUDY eCRF.

#### 4.1.5. Days on IMP

Days on IMP is the number of days from Day 1 to the date of last dose of IMP as recorded on the OVERALL DOSING - BLINDED eCRF.

#### 4.1.6. Baseline Value

For purposes of analysis, the baseline value is defined as the last value obtained prior to initiation of IMP. Should the Day 1 visit value be obtained after the first dose of IMP or if this value is not available at Day 1, then the most recent value obtained prior to earliest initiation of IMP will be used for the baseline value. For ECGs, baseline is the last non-missing value obtained prior to the initiation of IMP. If the last non-missing value is obtained at the screening visit, then the baseline is the average of the triplicates. For vital signs taken in triplicate, the baseline value will be defined as the average of the predose values on Day 1 (calculated separately for each collection position, if applicable). If the triplicate value is not available, then the last non-missing value obtained prior to the initiation of IMP will be used.

#### 4.1.7. Change from Baseline

Change from baseline for a given endpoint is defined as the value on a given Study Day (Time Point) minus the Baseline Value.

#### **4.1.8. Orthostatic Change**

Orthostatic change is calculated as the difference in the standing value from the supine value (i.e., supine value – standing value). If an average value is available at a given visit, date, timepoint, it will be used for the calculation of orthostatic change. If an average value is not available, the individual record obtained on a given visit, date, and timepoint will be used.

#### **4.1.9. Average Daily Dose of IMP**

The average daily dose of IMP is calculated in milligrams and is based on the daily dose of IMP as recorded in the OVERALL DOSING – BLINDED eCRF. The average daily dose will be calculated as the cumulative dose divided by the expected days on study treatment.

#### **4.1.10. Compliance with Study Drug**

The date and dose (and time on days with PK assessments) of each IMP administration, along with information on any missed or inappropriately administered dose, will be recorded in source documents and the eCRF. Compliance will be ensured by a hand and mouth check during the oral dosing administration. Compliance will be calculated as a percentage based on the total number of doses taken relative to the total expected number of doses based on days on treatment as recorded in the OVERALL DOSING – BLINDED eCRF.

